9.7. Data Analysis

9.7.1. Main analyses

Detailed methodology for summary and statistical analyses of data collected in this study will be documented in the SAP, which will be dated, filed, and maintained by the sponsor. The SAP may modify the plans outlined in the protocol; any major modifications would be reflected in a protocol amendment.

Data will be analysed in each country separately using a common protocol, database-specific definitions of the study variable, and common analysis strategies. Only data available in a given country will be analysed and presented (Table 1,Table 2). The results will be presented separately for each country.

For each country, patient baseline characteristics will be reported to the extent measured in each database, including demographics (age and sex), comorbidities (including asthma, food allergies, depression) and prior and current medication use (including treatments for atopic dermatitis and medications noted for interactions in the abrocitinib label as captured in outpatient dispensing data or other available secondary routinely collected data on medication use). Other characteristics frequently diagnosed among patients with atopic dermatitis may be added given acceptable validity and completeness measured via diagnoses or treatment proxies and known in time for inclusion in planned data extractions; existing

PFIZER CONFIDENTIAL

ethical and data protection permissions and the associated data applications may need to be amended to enable inclusion of additional variables.

Counts and proportions for categorical variables and mean, median with range or interquartile ranges (IQRs) for continuous variables will be reported to address the study objectives, as follows:

1) The count and proportion of patients with evidence of having performed the following laboratory tests and screenings within 3 months prior to initiation of abrocitinib:

- CBC including absolute lymphocyte count, absolute neutrophil count, platelet count and haemoglobin level
- Lipid panel (ie, total cholesterol, HDL, LDL, and TG)
- Screening for TB, and
- Screening for viral hepatitis B and C

2) The count and proportion of patients with evidence of having performed the following laboratory tests at week 4 (\pm 2 weeks) after initiation of abrocitinib:

- CBC including absolute lymphocyte count, neutrophil count, platelet count and haemoglobin level
- Lipid panel (i.e., total cholesterol, HDL, LDL, and TG)

3) The proportion of patients with evidence of having risk factors and the number of risk factors for VTE, MACE, malignancy excluding NMSC, NMSC, and serious infection (including age 65 years or older, estimated dose of >100 mg/day for patients ages 65 or older, history of atherosclerotic disease, malignancy, pregnancy, history of VTE, use of combined hormonal contraceptives or hormone replacement therapy, major surgery, inherited coagulation disorder, diabetes, history of serious or opportunistic infection, TB) within 6 months prior to initiation of treatment with abrocitinib

4) The count and proportion of patients with evidence of having received live attenuated vaccines (e.g., measles, mumps, rubella) 4 weeks prior to and during treatment with abrocitinib

5) The count and proportion (among all pregnant women identifiable in a given database) of women in whom pregnancy overlaps with abrocitinib use

6) The count and proportion patients identified with severe hepatic impairment up to 6 months prior to or during treatment with abrocitinib

7) The count and proportion of patients aged <12 years on the index date

PFIZER CONFIDENTIAL

Abrocitinib B7451085 NON-INTERVENTIONAL STUDY PROTOCOL Version 2.0, 23 May 2024 8) The count of proportion of patients with an estimated starting dose > 100mg/day, and a description of the duration of use (median and IQR)

All proportions will be reported with 95% CIs.

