Population The study population will include patients with a dispensing of abrocitinib as recorded in routinely collected electronic healthcare data in Denmark, France, Sweden, Spain and Hungary during the study period (study start: country-specific aRMM distribution [01

PFIZER CONFIDENTIAL

Abrocitinib B7451085 NON-INTERVENTIONAL STUDY PROTOCOL Version 2.0, 23 May 2024 March 2022, Sweden; 09 March 2022, Denmark; 31 July 2022, France; 30 Jan 2023, Spain; 05 April 2024, Hungary]; study end: December 2026). These countries have universal healthcare.

Variables The study will collect all relevant data including patient demographics, comorbidities, prescription medications, vaccine administration, and laboratory testing prior to the initiation of abrocitinib and during treatment with abrocitinib to address the study objectives.

Data sources This study will utilize routinely collected electronic healthcare data from national or regional population-based electronic healthcare registers in Denmark, Sweden, and Spain and an administrative healthcare databases in France and Hungary.

Study size All patients initiating abrocitinib during the study period will be included.

Data analysis Data will be analysed in each country separately using a common protocol, database-specific definitions of the study variable, and common analysis strategy. The main indicators will be proportions of abrocitinib users with a given indicator of aRMM adherence.

Milestones

Milestone	Planned date*
Registration in the HMA-EMA Catalogues of RWD Studies	To be registered before the start of data collection
Start of data collection	31 December 2024
End of data collection (the date from which the analytical dataset is completely available, i.e., clean and coded data from all participating countries/databases)	15 May 2028
Interim Report 1	15 November 2025
Interim Report 2	15 May 2027
Final study report	15 November 2028

* Subject to data delivery and application approval timelines by data custodians in participating countries

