8.2. Research objectives

The study objectives are to evaluate, to the extent measurable in the available routinely collected data, indicators of HCPs' adherence to the RMMs in accordance with the abrocitinib SmPC, prescriber's brochure and DHPC, specifically:

- Indicators of adherence to performing laboratory tests of CBC, lipid panel, hepatitis B/C and TB screening prior to initiation of abrocitinib treatment,
- Indicators of adherence to performing laboratory tests of CBC and lipid panel at week 4 (± 2 week) after initiation of abrocitinib treatment,
- Indicators of adherence to consideration of risk factors for VTE, MACE, malignancy excluding NMSC, NMSC, and serious infection prior to treatment with abrocitinib,
- Indicators of adherence to avoid live attenuated vaccines immediately prior to and during treatment with abrocitinib,
- Indicators of adherence to contraindications for use during pregnancy,
- Indicators of adherence to contraindications for use among patients with severe hepatic impairment,
- Indicators of adherence to no use in patients aged < 12 years, and
- Indicators of adherence to recommended posology (estimated average daily dose).

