9.2.1. Inclusion criteria

All patients with at least 1 dispensing of abrocitinib between study start (country-specific aRMM distribution [01 Mar 2022, Sweden; 09 Mar 2022, Denmark; 31 Jul 2022, France; 30 Jan 2023, Spain; 05 April 2024, Hungary]) and December 2026 in the participating databases will be eligible for inclusion in this study. The date of the first dispensing of abrocitinib will be the index date. Patients must meet the above inclusion criteria to be eligible for inclusion in the study.

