9.5. Study size

There is no minimum sample size planned in this study. This is a descriptive study and no comparative analyses will be conducted. Thus, the purpose of the sample size calculations provided below is to describe the precision of the estimates.

The following formula, based on the normal approximation to the binomial proportion, was used to calculate the sample size for this study:

$$n = \frac{P \cdot (1-P) \cdot \left(Z_{1-\alpha/2}\right)^2}{e^2},$$

Where *P* is the expected proportion of patients with evidence of having performed the recommended laboratory test prior to/during treatment with abrocitinib (e.g., CBC); *e* is the margin of error, or half the desired width of the confidence interval (CI); and $Z_{1-\alpha/2}$ is the standard normal *Z*-score corresponding to a cumulative probability of $1-\alpha/2$.

As the proportion of patients with evidence of having performed the recommended laboratory test prior to/during treatment with abrocitinib (p) is not known in advance, it will be set to 50%, which yields the most conservative (i.e., the largest) sample size for a specified margin of error. Therefore, to obtain 95% CIs with a desired width of 10% (half width of 5%) for each laboratory test, the study will require a sample size of at least

385 patients. Note that the proportion of patients with evidence of having performed the laboratory test will vary by test which will affect the precision as well (Table 3).

Table 3.Number of Abrocitinib Treated Patients by Proportion of Patients With
Evidence of Having Performed the Recommended Laboratory Test and
Width of 95% CI

Proportion of patients with evidence of having performed the recommended laboratory test	Width of 95% CI	Required Number of Patients
25%	0.10	289
	0.15	129
	0.20	73
50%	0.10	385
	0.15	171
	0.20	97
75%	0.10	289
	0.15	129
	0.20	73

Although the sample size identified to meet the aforementioned precision estimate requirements is 385, the study will include all patients identified during the study period who meet the eligibility criteria to maximize the precision of the estimates.

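### Item 3 of the main analyses gives the risk profile of treated patients; whether prescribers considered the risk factors cannot be identified from it

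*Protocol*

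**What the plan says.** Protocol section 8.2 lists as an objective "Indicators of adherence to consideration of risk factors for VTE, MACE, malignancy excluding NMSC, NMSC, and serious infection prior to treatment with abrocitinib". The PASS information table and the abstract carry the same objective.

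The only analysis that serves it is item 3 of section 9.7.1: "The proportion of patients with evidence of having risk factors and the number of risk factors for VTE, MACE" and the other listed risks. The listed factors are age 65 or over, atherosclerotic disease, malignancy, pregnancy, prior VTE, hormonal treatment, major surgery, inherited coagulation disorder, diabetes, prior serious or opportunistic infection, tuberculosis, and "estimated dose of >100 mg/day for patients ages 65 or older". All are to be ascertained "within 6 months prior to initiation of treatment with abrocitinib".

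The population in section 9.2.1 is "All patients with at least 1 dispensing of abrocitinib between study start" and December 2026, with no exclusions. Section 9.5 adds: "This is a descriptive study and no comparative analyses will be conducted". The abstract says of the analysis as a whole: "The main indicators will be proportions of abrocitinib users with a given indicator of aRMM adherence".

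**The concern.** Considering a risk factor is something a prescriber does. Item 3 records, almost entirely, what the patient has. Two patients with diabetes, one treated after careful weighing and one treated with none, score the same.

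The other adherence items do not share this problem. Items 1, 2 and 4 to 7 each have an evident direction: a test was done, a live vaccine was given, a pregnancy overlapped with use, a patient was under 12. For item 3 the protocol never says whether a high or a low value would speak for adherence, and it supplies nothing to compare the value with.

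Section 7 says the evaluation should show whether the programme's objectives were met or whether it needs changing. On this objective the study would deliver a precise number that supports either conclusion.

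**Working it through.** **The plan's own figure.** No precision figure is given for item 3. The figure in section 9.5 for laboratory tests reproduces: 0.5 × 0.5 × 1.96² / 0.05² = 384.15, rounded up to 385. With 385 patients and an observed 20%, the 95% half-width would be 1.96 × √(0.20 × 0.80 / 385) = 0.040, or 4.0 percentage points. Precision is not the difficulty.

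**What the proportion can identify.** The following inputs are assumptions; none is in the protocol.
- p0: prevalence of any risk factor among candidates for treatment.
- c: share of prescribing decisions in which risk factors are considered.
- d: share of at-risk candidates who are not treated once considered.
- s = c × d: overall share of at-risk candidates steered away.
- Candidates without risk factors are all treated.

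Item 3 then observes

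p = p0(1 − s) / (1 − p0·s), which gives p0 = p / (1 − s + p·s).

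For an observed p = 20%:

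| s | p0 that yields 20% |
|---|---|
| 0 | 0.20 / 1.00 = 20% |
| 25% | 0.20 / (0.75 + 0.05) = 25% |
| 50% | 0.20 / (0.50 + 0.10) = 33.3% |
| 75% | 0.20 / (0.25 + 0.15) = 50% |

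Without p0, the same result fits 0% to 75% steered away.

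Knowing p0 would not be enough either, because item 3 depends on c only through the product c × d:
- With p0 = 20%, an observed 20% means s = 0. That is c = 0 (nobody considers) or c = 1 with d = 0 (everyone considers and then treats).
- With p0 = 33.3%, an observed 20% means s = 0.5. That is c = 1 with d = 0.5, or c = 0.5 with d = 1.

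The quantity named in the objective is c. More patients narrow the interval around p and leave c as undetermined as before.

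**What the dose element adds.** Anyone who meets "estimated dose of >100 mg/day for patients ages 65 or older" is by definition aged 65 or over, which is itself on the list.
- Proportion with any risk factor: unchanged by the dose element.
- Number of risk factors: raised by one. A count of two may then mean age plus dose, or age plus diabetes, and the total does not say which.

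Coverage is also uneven. Section 9.3 excludes Hungary from dose analyses, and the notes to Table 2 derive dose in Spain from the WHO defined daily dose and the time between prescriptions.

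**The case against.** Four replies deserve weight.

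1. **The objectives are hedged.** They are worded as indicators, "to the extent measurable in the available routinely collected data", and the study is descriptive. This stands as a limit on ambition. It concerns what the data contain and gives no rule for reading item 3. Section 9.9 warns of under-recording, including of atherosclerotic disease. It does not say that a perfectly recorded prevalence would still fail to measure consideration.

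2. **Prescribers do influence item 3.** A reader might infer that nothing in it depends on the prescriber, so that no result could bear on adherence. The documents do not support that. Dose at age 65 or over is a prescribing choice and has its own row in Table 2. The formula also shows the prevalence falling as more at-risk patients are steered away. Pregnancy is listed too, although it bears on the separate contraindication objective handled in item 5. The sound claim is that consideration cannot be identified from item 3 as defined.

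3. **No misreading is written into the plan.** A reader might infer that a low prevalence will be reported as adherence and a high one as failure. No section sets such a rule. The abstract speaks of the main indicators collectively and does not label item 3 in particular. The fault is that no reading is given at all.

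4. **Details belong in the SAP.** Algorithms and look-backs do. The objective, and the analysis that answers it, are fixed in sections 8.2 and 9.7.1 of the protocol.

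A reader might also want to rescue the objective by comparing patients with and without risk factors on testing, dose or prior systemic therapy. That would not identify consideration. Testing is measured in all initiators, so full adherence would show no difference, and extra tests in patients with diabetes or cancer may be routine care. The protocol ties a dose threshold to risk only at age 65 or over. Such contrasts would also sit badly with section 9.5, which rules out comparative analyses.

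**Conclusion.** The point holds in this limited form. Item 3 is the prevalence and number of risk factors among treated patients, and it cannot show whether prescribers considered those factors, whatever the sample size. The 0% to 75% range at an observed 20% rests on assumed source prevalences of 20% to 50% and on a simple selection model. The conclusion does not depend on those values, since considering and then treating gives the same result as ignoring under any source prevalence. The single element that directly reflects a prescribing choice is placed where it cannot alter the proportion with any risk factor. One of eight objectives is affected; the other seven are untouched.

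**What to change.** 1. In the PASS information table, the abstract, section 8.2 and item 3 of section 9.7.1, describe this analysis as the risk profile of abrocitinib initiators. State there and in section 9.9 that the prevalence is not read as adherence or non-adherence to consideration of risk factors.

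2. Take the dose element out of the pooled risk-factor list and count. Report it separately, with patients aged 65 or over as the denominator and a 95% CI, in countries with usable dose data. Hungary is excluded, and Spain should be flagged because its dose is derived from the defined daily dose. The element needs its own time window, because a dose of abrocitinib cannot fall before initiation.

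No new data are needed. The cost is a protocol amendment that restates one objective, which matters because the study is an EMA commitment, plus one extra reported proportion. The objective is stated less strongly, and the cells for patients aged 65 or over may be small in some countries.

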9.3. Variables

The study will collect all relevant data including patient demographics (e.g., age and sex), comorbidities, prescription medications, vaccinations, procedures, and laboratory tests prior to initiating abrocitinib and while on treatment to address the study objectives. Abrocitinib and concomitant medications and vaccinations will be identified using ATC codes. Diagnoses will be recorded using diagnostic codes. Performance of laboratory tests, available from Denmark, will be identified using Nomenclature, Properties and Units (NPU) codes. Surgeries will be defined using country-specific procedure/surgery codes. Age (date of birth) and sex will be used as reported in the databases. The average daily dose of abrocitinib will be estimated using a combination of information available per country: strength of the prescription dispensed, packet size, World Health Organization (WHO) defined daily dose and duration of therapy (time between prescriptions/dispensings). Availability of specific data types varies by country. There is no information in Hungary available to estimate dose therefore this data source will not be included in analyses of dose.

The maximum lookback period for ascertaining characteristics before abrocitinib initiation will be 12 months (365 days), but will vary for a given RMM measure, per SmPC. Full country-specific algorithms for all study variables, including RMM-specific lookbacks will be specified in the SAP.

Table 1 summarizes the data available by country for analysis of patient co-morbidities, and prior and current medication use. Table 2 summarizes types of RMMs and specificity available by country for analysis. ANNEX 3. ADDITIONAL INFORMATION provides preliminary definitions of the codes to be used to define each element, per country.

Table 1. Availability of patient co-morbidities and concomitant medications in each country

	Denmark	France	Sweden	Spain 1	Hungary
Co-morbidities					
Acne	No	No	No	Yes	Yes
Allergic conjunctivitis	No	No	No	Yes	Yes

	Denmark	France	Sweden	Spain	Hungary
Allergic rhinitis	No	No	No	Yes	Yes
Anxiety	If treated in specialist care or through medication	No (unless hospitalized)	If treated in specialist care or through medication	Yes	Yes
Asthma	Identification of persisting asthma using hospital records and medication is possible.	Identification of persisting asthma using hospital records and medication is possible.	Yes	Yes	Yes

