9.4. Data sources

This study will utilize secondary routinely collected data from population-based electronic registers in Denmark, Sweden and Spain, and a nationwide healthcare databases in France and Hungary. These secondary data sources were selected based on the expected required data elements' availability and projected sample size/number of patients with abrocitinib exposure during the study period. The data sources for this study are described below:

Denmark: Denmark's population-based registers, linkable by a unique identifier, the central person registration (CPR) number, assigned to all residents at birth or upon immigration) contain routinely collected data for the country's entire population of 5.8 million individuals (11, 12). The Danish National Prescription Registry contains information on all prescription medicines dispensed at Danish community pharmacies with prescriptions, including vaccinations, recorded via Anatomical Therapeutic Chemical (ATC) codes. Prescriptions administered at specialist hospital-based clinics are captured in the Danish National Patient Register, and tentatively from 2023, in the Danish Hospital Medicines Register (currently in development (13)). Newly approved drugs, especially expensive treatments, are often first prescribed or administered at the specialist hospital clinics with follow-up with general practitioners. Such treatments (active substance) may be identifiable via treatment codes in the Danish National Patient Register. The Danish National Patient Register records diagnoses (WHO International Classification of Diseases (ICD)-10 and ICD-11 codes) and procedures (Nordic Medico-Statistical Committee [NOMESCO] codes) during inpatient or outpatient hospital encounters. Danish Cancer Registry has mandatory reporting of primary malignancies since 1987. Danish Register of Laboratory Results collects information on hospitalperformed laboratory tests. Danish Medical Birth Registry will be used to identify pregnancies ending in a live or stillbirth (14-21).

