Sweden: Similar to Denmark, the Swedish register system is a large, complete source of population-based data from the entire Swedish population (10.4 million in 2020). Data from the Swedish National Health Registers, including the National Patient Register, Prescribed Drug Register, Total Population Register, Swedish Cause of Death Register, and Swedish Medical Birth Register will be used. A unique personal identity number is issued to all residents of Sweden upon birth or immigration and is used unchanged throughout life. The personal identification number is used to link patient-level data across the various registers. All citizens, independent of socioeconomic status, have unrestricted access to healthcare services including partial or complete reimbursement of purchased medications due to the tax-supported public health service with universal coverage. The Swedish National Patient Register includes diagnosis information for inpatients at public hospitals and outpatient specialists visits, including primary and secondary diagnoses and surgical procedures. The Prescribed Drug Register includes information on outpatient dispensings of all prescribed drugs sold in Sweden since 01 July 2005. The register contains patient level data on dispensed medicines for the entire Swedish population, including information on the dispensed drug as well as the dates of prescription and dispensing (25-29). The Swedish Medical Birth Register will be used to identify pregnancies ending in live or stillbirth. The coding systems for diagnoses, procedures, and medications are similar in Denmark and Sweden.

Spain: The Information System for Research in Primary Care (SIDIAP) database includes primary care electronic health records for >8 million people in Catalonia dating back to 2006, with 5.8 million people active in June 2021 (30). SIDIAP is representative of the general population living in Catalonia in terms of age, sex and geographic distribution. SIDIAP includes high-quality data on demographics, all-cause mortality, disease diagnoses, prescription and dispensation of drugs, laboratory tests, socio-economic indicators, vaccinations, lifestyle information, parent–child linkage and clinical parameters.

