Hungary: Hungary has a single-payer healthcare system with a purchaser-provider split model and output-based payment system. The National Insurance Fund Administration (NHIFA) database contains information on healthcare covered by the state for over 9 million people in Hungary, and has national coverage for reimbursed services (medicine, out- and inpatient services) (31). Data are available for retrospective analyses from 01 January 2004. The NHIFA database includes information on demographics, mortality, Abrocitinib

B7451085 NON-INTERVENTIONAL STUDY PROTOCOL Version 2.0, 23 May 2024

prescribed drug codes, inpatient diagnostic and procedural codes, and outpatient lab, diagnostic services, and diagnostic codes.

There are four NHIFA registers: Demography, Drugs, Inpatient, and Outpatient. The Demography register includes sex, age, and date of death. The Drugs register captures brand information, date, ATC7 codes, volume, ICD codes, and territory. Further, information is collected regarding EU number, invented name, strength, pharmaceutical form, route of administration, packaging, and content. The Inpatient register comprises date (admission, discharge, and length of stay), location, ICD codes, Diagnosis Related Groups (DRG), and International Classification of Procedures in Medicine (ICPM) codes. The Outpatient register captures labs and diagnostic services and specialist visits, including date, location, ICD codes, and ICPM codes.

The research centres affiliated with this study and the associated data sources from Denmark, Sweden, France and Spain are listed in the European Network of Centres for Pharmacoepidemiology and Pharmacovigilance (ENCePP) Register (https://www.encepp.eu/encepp/viewResource.htm?id=42185, https://www.encepp.eu/encepp/viewResource.htm?id=42187, https://www.encepp.eu/encepp/viewResource.htm?id=2291, https://www.encepp.eu/encepp/viewResource.htm?id=41070, https://www.encepp.eu/encepp/viewResource.htm?id=38744)

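### Permanent and history-of risk factors are sought only in the 6 months before initiation, under a 12-month cap on any lookback, so older recorded history goes uncounted and item 3 is biased downward

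*Protocol*

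**What the plan says.** Protocol section 9.7.1, item 3, reports the proportion of patients with risk factors for VTE, MACE, malignancy, NMSC and serious infection, and how many such factors they have. The list includes "history of atherosclerotic disease, malignancy, pregnancy, history of VTE, use of combined hormonal contraceptives or hormone replacement therapy, major surgery, inherited coagulation disorder" and closes with "diabetes, history of serious or opportunistic infection, TB) within 6 months prior to initiation of treatment with abrocitinib". One time limit ends the whole list.

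Section 9.3 sets an outer bound: "The maximum lookback period for ascertaining characteristics before abrocitinib initiation will be 12 months (365 days". Below that bound the lookback may differ by measure, and "Full country-specific algorithms for all study variables, including RMM-specific lookbacks will be specified in the SAP". Section 9.7.1 adds: "The SAP may modify the plans outlined in the protocol; any major modifications would be reflected in a protocol amendment".

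Section 9.4 describes longer records. For Denmark, "Danish Cancer Registry has mandatory reporting of primary malignancies since 1987". For Hungary, "Data are available for retrospective analyses from 01 January 2004". For Spain, the source holds "primary care electronic health records for >8 million people in Catalonia dating back to 2006".

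**The concern.** A short window suits factors that come and go, such as hormone use, recent surgery or pregnancy. It does not suit factors that are permanent, or that item 3 itself labels as history. An inherited coagulation disorder does not lapse because nobody coded it in the last half-year. Under this rule, a history of VTE becomes a VTE record from the last 6 months, or from the last 12 at most.

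Item 3 is the analysis behind the third study objective, consideration of risk factors before treatment. For permanent and history-of factors, shortening the window can only remove patients from the count. The indicator would understate how often abrocitinib is started in patients with recorded risk factors. It would look as precise as any other proportion in the report.

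**Working it through.** **1. The plan's own figure.** Section 9.5 uses n = P(1−P)z²/e². With P = 0.50, e = 0.05 and z = 1.96, n = 384.15, which rounds up to the stated 385. All nine cells of Table 3 reproduce. The calculation covers sampling error only and does not involve the lookback.

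**2. What the text fixes.** Item 3 gives 6 months and section 9.3 gives a maximum of 12. The lookbacks left to the SAP therefore lie inside 12 months. If the 6-month phrase is read as attaching only to the last items in the list, the 365-day cap still binds the others.

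**3. How the factors are recorded.**
- Table 2 takes malignancy from cancer registers in Denmark and Sweden, and section 9.4 describes the Danish one as reporting primary tumours. A short window there mainly finds new diagnoses.
- Annex 3 defines serious infection as a primary diagnosis at a hospital contact with an overnight stay, which is a discrete event.
- Table 2 takes diabetes and atherosclerotic disease in Denmark and Sweden from in- and outpatient diagnoses. Section 9.4 places those registers in hospital or specialist care.
- In France, Table 2 uses Long Term Disease registration for malignancy, atherosclerotic disease and diabetes. This may act as a standing status that is visible inside a short window.

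**4. History available.** From the section 9.4 dates to each country's study start:
- Danish Cancer Registry: 1987 to 2022, about 35 years.
- Hungary: 2004 to 2024, about 20 years.
- Spain: 2006 to January 2023, about 17 years.

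**5. Share captured.** The documents do not say how recently, or how often, these diagnoses are recorded. Two illustrative models, with window L in years:

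(a) Recorded once, spread evenly over the T years before the index date: capture = min(1, L/T).

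| T (years) | L = 0.5 | L = 1 |
|---|---|---|
| 1 | 50% | 100% |
| 2 | 25% | 50% |
| 5 | 10% | 20% |
| 10 | 5% | 10% |
| 20 | 2.5% | 5% |

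(b) Re-coded at rate λ per year: capture = 1 − exp(−λL).

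| λ per year | L = 0.5 | L = 1 |
|---|---|---|
| 0.25 | 12% | 22% |
| 0.5 | 22% | 39% |
| 1 | 39% | 63% |
| 2 | 63% | 86% |
| 4 | 86% | 98% |

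More than half is missed at 6 months if T > 1 year or λ < ln 2/0.5 = 1.39. At 12 months the conditions are T > 2 years or λ < ln 2/1 = 0.69.

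**6. Effect on a reported proportion.** Assume a true prevalence of 10% and n = 385, so 38.5 patients carry the factor; a complete count would have a 95% half-width of 3.0 points.
- At 10% capture: 3.9 patients counted, reported 1.0%, half-width 1.96·√(0.01·0.99/385) = 1.0 point.
- At 50% capture: 19.2 patients counted, reported 5.0%, half-width 2.2 points.
- At 86% capture: reported about 8.6%.

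In the first two cases the interval excludes the true 10%.

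**7. Mitigation.** The sensitivity analyses in section 9.7.2 change the population (evidence of AD) and the study start date, not the lookback. Section 9.9 concedes that atherosclerotic disease may be underestimated, but attributes this to treatment in primary care.

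**The case against.** The best reply is that lookbacks are left to the SAP and may vary by measure. That does not cure the problem, because the maximum is set in the protocol and a SAP that follows it cannot reach older history.

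Other objections do limit what can be claimed:
- A reader might infer that most patients with such history are missed. The documents hold no recency or re-coding data. With frequent coding, or a standing status such as the French registration, the loss may be modest.
- A reader might infer that missed patients are classed as free of risk. They are only uncounted for that factor. They can still count through age, hormone use, surgery or another item.
- A reader might infer that the bias always favours a finding that the measures work. The protocol sets no success threshold, tests no hypothesis and does not say that a low proportion means success. Only undercounting follows.
- A reader might infer a uniform 6 months for every listed item. Age and abrocitinib dose are also in the list and cannot be ascertained that way. The firm constraint is the 365-day cap.
- A reader might infer that every database holds decades of diagnoses. Section 9.4 gives no start year for the French data or for the Danish and Swedish patient registers.
- A reader might extend the point to severe hepatic impairment in item 6. That item concerns a contraindication around the time of use, and nothing here argues for changing its window.

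Resolved serious infection is less clear-cut than a lifelong condition. Item 3 nevertheless calls it history, and the window does not deliver that.

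**Conclusion.** The point holds for permanent and history-of factors: VTE, atherosclerotic disease, malignancy and NMSC, inherited coagulation disorder, diabetes, serious or opportunistic infection, and TB. The direction follows from the text: the proportion and the number of risk factors are biased downward. The size rests on the assumed recording patterns above, and no document figure selects among them. The loss is likely to be largest for once-recorded events, such as cancer-register entries in Denmark and Sweden, an old VTE or a single thrombophilia code. It is likely to be smaller where a standing status exists. No figure in the protocol changes.

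**What to change.** Amend sections 9.3 and 9.7.1 together, before data extraction (start of data collection is planned for 31 December 2024):

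- Split item 3. For the permanent and history-of factors, use all history in each database before the index date, and remove the 365-day cap for them.
- Report the years of history available per country.
- Add one common fixed window as a supplementary analysis. Results are presented by country, but readers will compare them and history length differs.
- Keep the short window for hormone use, major surgery and pregnancy.

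The cost is protocol and SAP wording and a longer extraction window in the data permits. The remaining drawback is unequal history length across countries, which the reported years and the common window make visible.
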